2. Secondary obesity or diabetes.
3. Serious systematic diseases, such as digestive diseases, tumor, cardiac, pulmonary, renal, rheumatic and immune system diseases.
4. Pregnant women, women ready for pregnancy, and nursing mothers.
5. Take antibiotics or bacterial agents within 1 month
6. Diarrhea or abscess in 1 month or blood or other abnormal feces
7. Diabetics history more than 2 years
8. The OGTT experiment $FG \geq 9 \text{ mmol/L}$ or $2h \geq 14 \text{ mmol/L}$ in diabetic patients

Study settings

The interventions and laboratory tests and performed and managed at the Health Care Center, Southwest Hospital, Chongqing, and Health management institute, PLA General hospital, Beijing, China.

Trial design

Interventions

1. Probiotics group: Diabetes/prediabetes participants take four packs of probiotics a day on an empty stomach with 200ml water every morning. The probiotics is called KAWAI, each pack contains 880 billion dead *Lactobacillales* (*S. thermophilus*) .
2. Placebo group:
Diabetes/prediabetes participants take four packs of probiotics a day on an empty stomach with 200ml water every morning.

Primary and secondary outcomes

Primary outcomes:

1. Blood glucose levels(FBG and OGTT), insulin sensitivity(Insulin, C-peptide)
2. Gut microbiota composition

Secondary outcomes:

1. Blood inflammatory markers
2. Diabetes risk factors (blood pressure, blood lipids)
3. Weight, waist circumference, BMI, Body composition
4. Intestinal endocrine function (GPL-1)
5. Gut microbiota metabolites

The primary and secondary outcome measures will be assessed at baseline, 1- and 3-month time points.

Measurements procedures

1. Screening:

The potential subjects will be selected from the outpatient pool of those who have records of abnormal blood glucose level in 2017. Registered nurses from health care center will first contact the potential subjects and invite them to a

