study information meeting. Detailed information of the objectives of the study, its nature and constraints, the anticipated risks and the expected benefits are given by the investigating physician of endocrinology and professor of sport medicine in the recruitment information meetings. When the screening consent form has been signed, patients will be asked to fill in a screening questionnaire to check their health and medication background as well as alcohol consumption, and to undergo a glucose tolerance test (blood draw after overnight fasting, followed by samples of 2 hours after the intake of 75 g of glucose).

Follow-up visits

The purpose of the follow-up visits is to monitor the compliance, enhance retention of the subject in the study, and obtain information on factors that may affect outcomes of the study. A study coordinator will contact participants every month to check their oral probiotics records. The study coordinator will also give feedback. The participants will have follow-up visits to the laboratory of Health care Center, Southwest Hospital, Chongqing at months 1, 3. Their height, weight, blood pressure, blood samples, fecal samples, and changes in health status and body composition will be checked at those time points.

Methods of measurements

1. Questionnaire, anthropometry and physical examinations

Background information regarding lifestyle, behavioral and motivational characteristics as well as medical history will be collected by questionnaires. Data gathered from eligible subjects will then be used to describe the study populations, and individual results will be used to screen the changes and for monthly feedback.

Height will be determined using a wall-fixed measuring device, and weight using a calibrated scale. Height and weight will also be used to determine body mass index (BMI, weight(kg)/(height(m))²). Blood pressure will be measured after 5 min rest. A physician will examine the physical conditions of subjects and ensure that subjects meet the inclusion criteria.

2. Blood samples

Glucose tolerance tests will be performed after overnight fasting and 2 hours

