Randomization methods

1. Randomization Process:

SPSS will be used for generating the randomization assignment for Diabetes groups and prediabetes groups respectively. Randomization numbers will be generated and sealed in an envelope and kept by the study coordinator. On the basis of subjects' enrolment time when 20 qualified subjects are reached, the study coordinator will open one block to allocate subjects into each group.

2. Blinding:

Both subjects and investigators will be blinded with respect to the randomization assignment of each participant. The investigators will remain blinded until the completion of the study. The study coordinator will be blinded from which group the participants are signed in. The accuracy of the randomization log is the responsibility of the study coordinator.

Statistical methods

All data collected by questionnaires will be entered into database management software (EpiData), double checked by independent researchers, and exported to SPSS statistics version. If data is not normally distributed, their natural logarithms will be used for further analysis.

Descriptive statistics will be used to present the background and anthropometric data at the baseline and follow-up assessments as mean and 95% confidence interval (CI) unless otherwise stated.

An intention-to-treat (ITT) analysis will be performed to compare the Probiotics group to Placebo group. The effects of the interventions will be assessed using analysis of variance (ANCOVA) for repeated measures (treatment group \times time) and baseline difference as a covariate. If the significance of the group by time interaction is $p < 0.05$, the effect will be localized utilizing Bonferroni for multiple comparisons. The level of statistical significance chosen for the contrasts will be $p < 0.05$. In addition to the ITT

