analysis, efficacy or active treatment analysis will be done when the compliance of the participation of the intervention is $\geq 60\%$ of the whole trial [ANCOVA for repeated measures (treatment group \times time) and baseline difference as a covariate.] The percentage differences (0–3month) will be calculated from duration between baseline and end point measurements for each individual. The comparison of percentage changes in different groups will be performed using ANCOVA (two factor interactions: compliance/noncompliance \times treatment group) controlled for the baseline value using Bonferroni for multiple comparisons. If the significance of the overall group difference is $p < 0.05$, then the effect will be localized by contrast to the Con group. When the 95% CI does not include zero, the difference is regarded as statistically significant at $\alpha = 0.05$.

Linear Pearson's correlation, partial correlation, Kendall Tau's, and bivariate, logistic, and multivariate regression analysis will be used for analysing relationships. In addition, systems biology approaches will be used to develop models which integrate the different types of data and the high-throughput data measured in terms of gut microbiota composition, as well as LPSs and inflammation.

Ethical issues, research permits or information permit applications

The current study will continue to adhere to all relevant guidelines for good scientific and clinical practice. All subjects in this study are volunteers. None of the measurements are known to have any significant health risk.

The benefits and associated risks of the study will be carefully explained to the subjects and voluntary participation will be stressed. Informed consent will be obtained from all subjects. The study physician will be available during the laboratory tests. The study has been approved by Ethics Committee of PLAGH, (S2016-068-01).

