## Statistical plans

All data collected by questionnaires will be entered into database management software (EpiData), double checked by independent researchers, and exported to SPSS statistics version. If data is not normally distributed, their natural logarithms will be used for further analysis.

Descriptive statistics will be used to present the background and anthropometric data at the baseline and follow-up assessments as mean and 95% confidence interval (CI) unless otherwise stated.

An intention-to-treat (ITT) analysis will be performed to compare the Probiotics group to Placebo group. The effects of the interventions will be assessed using analysis of variance (ANCOVA) for repeated measures (treatment group  $\times$  time) and baseline difference as a covariate. If the significance of the group by time interaction is  $p < 0.05$ , the effect will be localized utilizing Bonferroni for multiple comparisons. The level of statistical significance chosen for the contrasts will be  $p < 0.05$ . In addition to the ITT analysis, efficacy or active treatment analysis will be done when the compliance of the participation of the intervention is  $\geq 60\%$  of the whole trial [ANCOVA for repeated measures (treatment group  $\times$  time) and baseline difference as a covariate.] The percentage differences (0–3month) will be calculated from duration between baseline and end point measurements for each individual. The comparison of percentage changes in different groups will be performed using ANCOVA (two factor interactions: compliance/noncompliance  $\times$  treatment group) controlled for the baseline value using Bonferroni for multiple comparisons. If the significance of the overall group difference is  $p < 0.05$ , then the effect will be localized by contrast to the Con group. When the 95% CI does not include zero, the difference is regarded as statistically significant at  $\alpha = 0.05$ .

Linear Pearson's correlation, partial correlation, Kendall Tau's, and bivariate, logistic, and multivariate regression analysis will be used for analyzing relationships. In addition, systems biology approaches will be used to develop models which integrate the different types of data and the high-throughput data measured in terms of gut microbiota composition, as well as LPSs and inflammation.

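### The only planned comparison of 0–3 month percentage change crosses treatment with post-randomization compliance, has its own p < 0.05 rule, and is not labelled supportive

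*Protocol*

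**What the plan says.** The Statistical methods section of the protocol and the Statistical plans section of the SAP carry the same text. It sets out three analyses in sequence.

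- **Intention to treat.** "An intention-to-treat (ITT) analysis will be performed to compare the Probiotics group to Placebo group". The model is a repeated-measures ANCOVA with treatment group by time and a baseline covariate. It has no compliance term.
- **Compliance-restricted analysis.** "In addition to the ITT analysis, efficacy or active treatment analysis will be done when the compliance" reaches 60% of the trial. It uses the same repeated-measures model.
- **Percentage change, month 0 to month 3.** "The comparison of percentage changes in different groups will be performed using ANCOVA (two factor interactions: compliance/noncompliance" by treatment group, "controlled for the baseline value using Bonferroni for multiple comparisons". A decision rule follows: "If the significance of the overall group difference is" below 0.05, the effect is located by contrast with the control group. A 95% confidence interval that excludes zero counts as significant at 0.05.

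The protocol's Follow-up visits section shows how compliance is learned: "A study coordinator will contact participants every month to check their oral probiotics records". Its Primary and secondary outcomes section lists the first primary outcome as "Blood glucose levels(FBG and OGTT), insulin sensitivity(Insulin, C-peptide" and does not name percentage change as an outcome.

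**The concern.** Compliance is observed during follow-up. A model that splits each arm by compliance and then averages the treatment difference over the strata compares subgroups formed after randomization. If compliance, or its relation to prognosis, differs between arms, those subgroups are no longer balanced by design and an inert product can appear to act. If compliance behaves alike in both arms there is no such bias, but averaging a large stratum with a small one can cost precision and change what is being estimated.

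Percentage change is an easily quoted effect summary, and here its only p-value would come from this model. A reader could take it as the percentage effect of the product, and the plan does not say how to read it if it disagrees with the intention-to-treat analysis. Two details needed to run it are also open: whether the 60% cut-off defines the compliance factor, and how the two strata are weighted.

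**Working it through.** **1. Reading the text.** The phrase that marks an analysis as additional to the intention-to-treat analysis is attached to the compliance-restricted analysis. The percentage-change sentences that follow stand on their own, use a different variable and carry their own significance rule. No other sentence in either document compares percentage change, so there is no by-arm version and no ranking.

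**2. The plan's own figure.** Sample size estimation gives 68 evaluable per prediabetes group and a joint 15% allowance for compliance and drop-out: 68 / (1 − 0.15) = 80, as stated, so 160 in total. The documents give no separate compliance rate. The rates below are assumptions, shown as a range.

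**3. Precision, if strata are weighted equally.** Take n per arm, a compliant proportion c in both arms and unit outcome variance. The estimate is 0.5 × (complier difference + non-complier difference). Its variance is 0.25 × [2/(nc) + 2/(n(1 − c))], against 2/n by arm. The ratio is 1 / [4c(1 − c)], and the effective sample is 160 × 4c(1 − c).

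| c | Variance ratio | Effective sample out of 160 |
|---|---|---|
| 0.70 | 1 / 0.84 = 1.19 | 134 |
| 0.85 | 1 / 0.51 = 1.96 | 82 |
| 0.90 | 1 / 0.36 = 2.78 | 58 |

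**4. What is estimated.** Suppose compliers gain an effect d and non-compliers gain none. Equal weights report 0.5 × (d + 0) = 0.5d at any compliance rate. The by-arm comparison reports c × d, which is 0.85d at 85% compliance.

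**5. False positives for an inert product.** Null simulation: 80 per arm, 20,000 trials per scenario, Monte Carlo standard error about 0.15 percentage points. Assumed correlations are 0.5 between prognosis and outcome and 0.5 between prognosis and latent compliance. The baseline value correlates r with prognosis. The model contains treatment, compliance, their interaction and baseline; the r = 0 case was run without the covariate. The outcome is a generic continuous variable, not a percentage change as such.

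| Scenario | Weights | r = 0 | r = 0.5 | r = 0.7 | r = 1 |
|---|---|---|---|---|---|
| Alike in both arms, 85% / 85% | equal | 4.6% | 4.8% | 5.0% | 5.1% |
| 75% vs 90% compliance | equal | 6.7% | 5.8% | 5.3% | 5.1% |
| 75% vs 90% compliance | size | 7.0% | 6.1% | 5.8% | 5.3% |
| Link to prognosis in one arm only, 85% / 85% | equal | 10.9% | 8.5% | 7.0% | 5.1% |

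For the last scenario, size weights give 4.8–5.1%. For the first, they give 5.1–5.3%. The by-arm comparison gives 4.8–5.3% throughout. The largest bias with equal weights is 0.092 SD (75% vs 90%) and 0.161 SD (one-arm link), both at r = 0. Both fall to zero at r = 1.

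**6. Empty cells in the diabetes stratum.** The chance that at least one arm has no non-compliers, so that the interaction cannot be estimated, is 1 − (1 − cⁿ)². The protocol gives 30 per diabetes arm under Trial design and 60 per diabetes group under Sample size estimation, so both are shown.

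| c | n = 30 | n = 60 |
|---|---|---|
| 0.85 | 1.5% | 0.01% |
| 0.90 | 8.3% | 0.4% |
| 0.95 | 38.3% | 9.0% |

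**The case against.** The strongest reply is that the plan already ranks its analyses. Intervention effects are assigned first to the intention-to-treat model, and what follows can be read as one supplementary block on compliance, with 60% as the only cut-off in the documents. That reading is possible, but the text does not state it, and a separate significance rule for percentage change points the other way.

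Several other points stand and limit the consequence:

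- No named outcome is defined as a percentage change. The primary glucose and insulin measures go through the intention-to-treat model.
- For outcomes that are log-transformed, that model is already a baseline-adjusted relative comparison by arm. This does not help untransformed outcomes.
- The trial is blinded ("Both subjects and investigators will be blinded with respect to the randomization assignment of each participant"), which makes differential compliance less likely. The plan also adjusts for baseline, which shrinks any bias.
- The precision loss and the halved effect arise only with equal weights. The 10.9% figure needs equal weights, a link to prognosis in one arm only, and no baseline adjustment. The 38% figure needs 95% compliance. Under milder assumptions (80% vs 85% compliance, correlation 0.3 with compliance in both arms, 6,000 trials per scenario) equal weights give 5.0–5.7% against 4.8–5.5% by arm, with bias of at most 0.015 SD.
- The plan applies Bonferroni within this comparison. That addresses multiplicity, not conditioning on compliance, and it does not rank the result against the intention-to-treat analysis.

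**Conclusion.** The concern holds. The plan gives percentage change a single model, conditioned on a post-randomization variable, with its own claim of significance and no supportive label. A baseline-adjusted comparison by randomized arm is a better method, and choosing it is more than filling in a missing detail.

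The size is modest. The intention-to-treat analysis of outcome levels still gives the randomized answer. With compliance alike in both arms, the false-positive rate stays at about 5% and the loss is in precision (variance up by a factor of 1.19 to 2.78 for 70% to 90% compliance, if strata are equally weighted) and in interpretation. Inflation appears only if compliance or its link to prognosis differs by arm, and under the assumptions tabulated above it does not exceed 10.9%. All these figures rest on assumed compliance rates, correlations and weighting that the documents do not give. The change should be made because it is cheap and removes the ambiguity; the main analysis is not in danger.

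**What to change.** Amend the percentage-change paragraph in the protocol and the SAP as follows:

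- Compare the month 0 to month 3 percentage change by randomized arm, with the baseline value as covariate and no compliance factor.
- For outcomes the plan log-transforms, analyse ln(month 3) adjusted for ln(baseline) and report the ratio between arms.
- Label both the compliance-by-treatment model and the 60% compliance analysis as supportive. Use one definition of compliance for both, state how the compliance strata are weighted, and rest no efficacy conclusion on either.

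The cost is wording only; no new data are needed. The one downside is that the compliance analysis loses its own significance claim.

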STUDY PROTOCOL

Effect of probiotics on T2DM and pre-diabetes in China ---the role of gut microbiota composition

Background

According to recent surveyed, diabetes prevalence rate in Chinese adults had gone up to 11.6%, the pre-diabetics diabetes prevalence rate was 50.1%. Effective intervention is urgently needed. Study of relationship between intestinal flora and diabetes is a hot topic at present. Gut microbiota disorders may be involved in the development of diabetes by means of increasing the number of inflammatory mediators, chronic inflammation, insulin resistance, increased energy intake, and obesity ect. In view of the correlation between gut microbiota and diabetes, gut microbiota can be taken as an important target for diabetes intervention. In this study, we aim to explore whether probiotics intervention affect blood glucose level and Risk factors for diabetes in T2DM and pre-diabetes via modification of gut microbiota composition and other post-interventional effects.

Objectives :

1. To investigate the effects of probiotics intervention on blood glucose metabolism (blood glucose, insulin sensitivity) and diabetes risk factors (blood lipid, weight, body composition, inflammatory state) in diabetes and pre-diabetes.
2. To investigate the effect of probiotics intervention on gut microbiota composition and its correlated metabolite.
3. To investigate the mediating effect of gut microbiota on glucose control in diabetes and pre-diabetes.

Methods/design

Trial design

This is a four-arm randomized controlled trial (Diabetes-intervention n=30, Diabetes-control n=30, prediabetes-intervention n=80, prediabetes-control n=80) . Participants are recruited from the outpatient registration pool of those who have participated in annual health checks for diabetes during 2017 to 2018 at Health care Center, Southwest Hospital, Chongqing, China. After an initial screening, potential subjects will be assessed for inclusion in the run-in trial. Those subjects who meet the inclusion criteria will be then invited to the intervention study for a total duration of 3 month. Those participants who are qualified for the intervention study will be randomized into intervention or control group after baseline assessments.

Eligibility criteria

Inclusion criteria:

1. The patient was diagnosed with pre-diabetes or diabetes by OGTT
2. Age: 18-60y
3. BMI:18-35kg/m²

Exclusion criteria:

1. Patients who have diabetes, hyperlipemia , and need regular use of drugs.

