after the intake of 75 g glucose for the assessment of serum insulin, and glucose. Venous blood samples will be taken in standardized fasting conditions at 7–8 a.m. Total cholesterol, high-density lipoprotein (HDL), low-density lipoprotein (LDL), triglycerides, will be measured from serum sample by conventional methods. ELISA can be used to assess serum samples for adiponectin, tumor necrosis factor alpha (TNF α), C-reactive protein (CRP), interleukin (IL-6), interleukin 10 (IL-10), and lipopolysaccharides (LPS). Gut microbiota metabolites will be measured from serum sample by LC-MS/MS.

3. Fecal samples collection

The fecal samples (two samples per each time) will be collected in the health care center during the second day of the 3-day dietary records collection. The study will provide to subjects the materials for sample collection. The subjects are advised to sample approximately 2–3 grams of feces by spatula attached to the cover of the plastic specimen jar. Fecal samples are frozen after collection within 30 min, stored at -80°C . 16SrDNA sequencing will be performed. Different bacterial indices will be calculated to evaluate the interrelationship of different bacterial species and how they are associated with diabetes.

4. Body composition

Bioelectrical impedance analysis will be used to estimate lean tissue mass (LM), fat mass (FM) and bone mass (BM) of the whole body, legs, arms, and trunk as well as android and gynoid regions.

Concomitant adherences and procedures

To ensure good compliance in probiotics and placebo group, we will keep in contact with them via phone call monthly questionnaire to check on their physical condition and lifestyle at 1 and 3months follow-up during the intervention.

Sample size estimation

The sample size calculation with an estimate of how many participants will be needed for the primary outcome to be statistically, clinically and/or politically significant. For the specific primary outcome of blood glucose and microbiota, based on our pilot study, 68 prediabetes subjects in each group would have 85% power for mean comparison between the randomized groups for the fast

blood glucose. We set the significance level at 0.05 and allowed for 10 mean comparisons with the Bonferroni correction between the groups. Taking into account the compliance and drop-out (15%), we increase our sample size to 80 in each prediabetes group. With the same approach, sample size for each diabetes group is 60 subjects.

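### The plan names no compositional method for the 16S data, so correlations between taxa can be artefacts of closure and a true glucose link of an abundant taxon can spread to unrelated taxa

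*Protocol*

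**What the plan says.** Protocol, Methods of measurements, item 3 (Fecal samples collection): "16SrDNA sequencing will be performed", followed by "Different bacterial indices will be calculated to evaluate the interrelationship of different bacterial species and how they are associated with diabetes". The indices are not defined, and no absolute quantification is mentioned.

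Protocol, Primary and secondary outcomes, lists "Gut microbiota composition" as the second primary outcome. The third objective is "To investigate the mediating effect of gut microbiota on glucose control in diabetes and pre-diabetes".

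Protocol, Statistical methods, gives the association methods: "Linear Pearson's correlation, partial correlation, Kendall Tau's, and bivariate, logistic, and multivariate regression analysis will be used for analysing relationships". The SAP, Statistical plans, repeats this without further detail: "Linear Pearson's correlation, partial correlation, Kendall Tau's, and bivariate, logistic, and multivariate regression analysis will be used for analyzing relationships". Both then add unspecified systems-biology modelling that is to integrate the microbiota data with other measurements. The only transformation in either document is the natural logarithm for data that are not normal. Neither document says whether taxa enter as counts, proportions or log-ratios.

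**The concern.** Without a measure of total bacterial load, 16S reads give each taxon's share of a total. When one share rises, the others must fall. This has two consequences.

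- **Taxon with taxon.** Zero is no longer the right null value for a correlation between two shares, even if the absolute abundances are independent.
- **Taxon with glucose.** Glucose lies outside the composition, so closure alone creates no link. If an abundant taxon is truly related to glucose, however, every other share moves the opposite way and can take on a false link of opposite sign.

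At stake are the planned statements on how species relate to each other and to diabetes, and any taxon-level evidence brought to the mediation objective. The randomised comparison of glucose is not affected.

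**Working it through.** The plan gives no figure to reproduce on this point. The check is of the mechanism and its size.

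**Inputs.** n = 160, the planned prediabetes participants (80 + 80; Protocol, Trial design), arms pooled. The rest are assumptions, because the documents do not give them: number of taxa K, share of the dominant taxon, log SD, and a correlation of 0.4 between one taxon and glucose. Absolute abundances are independent log-normal variables divided by their sum. Tests are two-sided at 5%, so a sound method should flag about 5% of unrelated pairs.

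**Set A: 10, 20 or 40 taxa; dominant share 20% or 40%; log SD 0.7 or 1.2.** False taxon-glucose links when only the dominant taxon is related to glucose:

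- proportions: about 9% to 35%
- logged proportions: about 14% to 43%
- centred log-ratio (CLR): about 5% to 10%

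False taxon pairs on proportions ranged from 4% to 26%. With no dominant taxon and 20 to 40 taxa, the figures were 5% to 6% for glucose and 2% to 7% for pairs. With no taxon linked to glucose, the glucose figure was 4% to 6% in every setting.

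**Set B: 5, 20 or 100 taxa; log SD 1; 1,500 replicates.** Here the dominant taxon is stronger. At the medians its share is e²/(e² + 4) = 7.39/11.39 = 65% for K = 5, e³/(e³ + 19) = 20.1/39.1 = 51% for K = 20, and e^4.6/(e^4.6 + 99) = 99.5/198.5 = 50% for K = 100.

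Percentage of unrelated taxa falsely linked to glucose, first taxon truly related (r = 0.4):

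| K | Dominant taxon | Pearson, proportions | Kendall | Pearson, logs | Pearson, CLR |
|---|---|---|---|---|---|
| 5 | no | 17.9 | 18.7 | 20.8 | 22.0 |
| 5 | yes | 57.6 | 68.3 | 72.7 | 20.6 |
| 20 | no | 6.3 | 5.0 | 5.4 | 5.7 |
| 20 | yes | 29.2 | 44.5 | 48.9 | 5.8 |
| 100 | no | 4.5 | 4.5 | 5.0 | 4.9 |
| 100 | yes | 26.5 | 43.1 | 47.7 | 5.0 |

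With no taxon related to glucose, every entry lies between 4% and 7%.

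Percentage of unrelated taxon pairs falsely linked (two non-dominant taxa):

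| K | Dominant taxon | Pearson, proportions | Kendall | Pearson, logs | Pearson, CLR |
|---|---|---|---|---|---|
| 5 | no | 94.1 | 66.0 | 53.9 | 89.3 |
| 5 | yes | 1.2 | 38.5 | 50.0 | 88.9 |
| 20 | no | 4.9 | 6.5 | 6.8 | 10.9 |
| 20 | yes | 7.1 | 36.5 | 43.2 | 11.9 |
| 100 | no | 3.3 | 5.3 | 5.3 | 5.8 |
| 100 | yes | 13.2 | 40.5 | 47.6 | 5.3 |

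**Why the log does not help.** The log of a share is log(own abundance) − log(total). With a dominant taxon the total follows that taxon, so each other taxon carries its signal with the sign reversed.

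**Why CLR helps only with enough taxa.** CLR subtracts the mean log over the K taxa. With equal log SDs, an unrelated taxon then has correlation −0.4/√(K(K − 1)) with glucose, and two unrelated taxa have correlation −1/(K − 1). The false-positive rate is about Φ(δ − 1.96) + Φ(−δ − 1.96), with δ = atanh|r| × √157:

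| K | r with glucose | False rate | r between taxa | False rate |
|---|---|---|---|---|
| 5 | −0.089 | 20% | −0.250 | 89% |
| 6 | −0.073 | 15% | −0.200 | 72% |
| 10 | −0.042 | 8% | −0.111 | 29% |
| 20 | −0.021 | 6% | −0.053 | 10% |
| 100 | −0.004 | 5% | −0.010 | 5% |

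These agree with the simulated CLR columns. CLR is close to nominal for glucose from about 20 taxa, and is no cure for taxon pairs when taxa are few.

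**The case against.** The strongest reply is that the plan does not say what it is being faulted for. The sentence on associations names no variables, and it also covers glucose, insulin, lipids, cytokines and LPS. The bacterial indices are undefined and could be diversity measures or ratios of taxa, to which the closure argument does not apply in the same way. The only method tied by name to microbiota data is the systems-biology modelling. This stands in part. A reader might infer that the plan prescribes Pearson correlation on proportions, and the documents do not say so. But they promise species-to-species and species-to-diabetes relations and name no other specific method that could deliver them, so use on taxa is a fair inference.

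A reader might also infer that unrelated taxa will generally appear linked to glucose. That is not supported: a false link needs another taxon, chiefly an abundant one, that is truly related to glucose. Nor are false taxon pairs universal, since with many evenly abundant taxa the rate is near nominal.

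A third tempting reading is that the second objective rests on these correlations. It is mainly a randomised comparison of composition, and only its metabolite part touches correlation. The third objective is mediation, for which no method is named; that is a separate gap.

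Finally, CLR is not a general remedy, as the rates at 5 and 6 taxa show. That stands and limits the fix.

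**Conclusion.** The concern holds in conditional form. The plan intends taxon-level association analyses on 16S data, names only ordinary correlation and regression for them, and states no compositional method. Its one transformation, the natural log, gave more false glucose links than untransformed proportions in the settings with a dominant taxon.

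If an abundant taxon is truly related to glucose, roughly 9% to 35% of unrelated taxa would be falsely significant on proportions and 14% to 43% on logs, against 5% to 10% on CLR values. This assumes n = 160, 10 to 40 taxa, a dominant share of 20% to 40% and r = 0.4. With no true taxon-glucose link, or with 20 or more even taxa, the rate is near 5%. The actual abundance profile is unknown, so the size in this trial cannot be fixed from the documents. The change should be made because it is cheap and the analyses are planned, but it does not bear on the glucose efficacy result.

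**What to change.** In the Protocol (Fecal samples collection; Statistical methods) and the SAP (Statistical plans):

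1. State the form in which taxa enter the analysis and the taxonomic level.
2. For taxon-to-clinical correlations and regressions, use centred log-ratio values after a stated zero replacement, at a level with about 20 or more taxa and not at phylum level.
3. For taxon-to-taxon relations, use a compositional measure such as SparCC or proportionality. Neither was tested in the calculations above.
4. Keep Pearson and Kendall for non-compositional variables such as diversity indices, cytokines, LPS and glucose.

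The cost is wording and a standard transform, with no new samples or visits. The downsides are that coefficients become log-ratios, which are harder to explain, and that software other than SPSS is needed. These changes do not settle how taxa are compared between the randomised groups; the form of the data should be stated there too, but no calculation here bears on it.
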